3.2 Randomization

Randomization occurred after informed consent was obtained. We concealed allocation and used a central randomization process. We used a web-based, secure randomization service (<http://www.randomize.net/>). After informed consent, the site research coordinator logged in to the website, registered the patient, and received the randomized assignment, ensuring allocation concealment. Patients were stratified by center and age (≥ 65 vs. < 65 years old).

Interventions and comparator

Intervention (Cycling): Patients were randomized to receive 30 minutes/ day of in-bed cycling in addition to routine physiotherapy interventions, 5 days per week, during their ICU stay. Cycling occurred for a maximum of 28 days or stopped when the patient could march on the spot for 2 consecutive days, whichever occurred first.

Comparator (Routine): Patients received routine physiotherapy interventions per current institutional practice. Routine PT included, based on the patient's alertness and medical stability, activities to maintain or increase limb range of motion and strength, in- and out-of-bed mobility, ambulation, and assistance with optimizing airway clearance and respiratory function.[4, 10-12]

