We will report the following adverse events if they occurred during or immediately after in-bed cycling or routine physiotherapy interventions, if they were attributable by the clinical team to the randomized intervention, and resulted in a clinical deterioration of the patient's status [3, 7, 39-41]:

Severe adverse events: unplanned extubation, cardiac arrest, or fall to knees during routine PT/ rehabilitation activities.

Serious adverse events: Concern for myocardial ischemia or suspected new unstable/ uncontrolled arrhythmia; Sustained symptomatic bradycardia (<40 bpm) or tachycardia (>140 bpm) and clinical deterioration attributed to in-bed cycling or routine PT/ rehabilitation activities; Sustained hypertension (mean arterial pressure >120 mmHg) and clinical deterioration attributed to in-bed cycling or routine PT/ rehabilitation activities; Sustained O₂ desaturation below baseline and clinical deterioration attributed to in-bed cycling or routine PT/ rehabilitation activities; Marked ventilator dyssynchrony; Bleeding at femoral catheter site attributed to in-bed cycling or routine PT/ rehabilitation activities; New bruising at femoral catheter site attributed to in-bed cycling or routine PT/ rehabilitation activities.

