6.5 Harms

For the safety analysis, we will only include the days on which the patients received the randomized intervention (i.e., days at risk of a safety event associated with rehabilitation

activities). We will report the frequency and percentage of patients with severe and serious adverse events, by group. We will also report the frequency and percentage of randomized intervention days with severe and serious adverse events, by group.

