Patient-reported functional scale for the ICU [56]					X		X	X
Physical Strength and Function:				X	X	X (blinded)	X (blinded)	
Physical Function ICU Test (scored)[14, 15]				X	X	X (blinded, Primary)	X (blinded)	
Medical Research Council Sum Score[49]				X	X	X (blinded)	X (blinded)	
30-second sit to stand[26]				X	X	X (blinded)	X (blinded)	

CYCLE Statistical Analysis Plan

	Study Period							
	Enrolment	Allocation	Post-allocation					
Timepoint	ICU admission	0	In ICU	ICU awakening	ICU D/C	3 days post-ICU D/C	Hospital D/C	90 days post-randomization
2-minute walk test[28]					X	X (blinded)	X (blinded)	
Psychological distress: Intensive Care Psychological Assessment Tool [31]				X				
Health-related Quality of Life: Euro-QOL 5D-5L[33, 34]					X		X	X
Hospital Anxiety and Depression Scale [36]								X
Data Collection:								
Baseline demographics	X							
Co-interventions			Document daily on CRFs					
Study-related Serious Adverse and Adverse Events			Document daily on CRFs					
Duration of mechanical ventilation								
ICU and Hospital Length of Stay							X	
Mortality					X		X	X

Supplement 2: Scoring algorithm for incomplete data in the PFIT-s

To account for incomplete component data in the PFIT-s, we will concurrently consider data from the PFIT-s, 30s sit-to-stand, and 2-minute walk tests at 3 days post-ICU or relevant time point (i.e., ICU awakening, ICU discharge, hospital discharge). For each patient with incomplete PFIT-s component data, we will evaluate the item within the context of the other scored PFIT-s items. For example, if a patient had a knee strength PFIT-s score of 1 or less (reflecting a Medical Research Council score of 3 or less and representing an inability to complete movement against gravity with any resistance), and had incomplete data for the sit-to-stand assistance component, then we would code sit to stand a score of 0, as this patient would likely not have the strength to stand. Likewise, if a patient completed the sit-to-stand component, needed assistance from 2 or more people, and data for step cadence were incomplete, we would assign step cadence a score of 0, as this patient would likely not have the strength to take any steps. In contrast, if a patient required 1 person to stand, and data for step cadence were incomplete, we would code this as missing data, as we do not have enough information to assess this patient's ability to perform the assessment.

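### Section 6.5 leaves Cycling-arm days with physiotherapy but no cycling out of the safety analysis, so event counts and patients with events can only be unchanged or too low in that arm

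*SAP*

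**What the plan says.** SAP section 6.5 sets the days for the safety analysis: "we will only include the days on which the patients received the randomized intervention". It describes these as "days at risk of a safety event associated with rehabilitation" activities. Two summaries follow for each group: the number and share of patients with severe and serious adverse events, and the number and share of intervention days with such events.

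Section 3.2 defines what each arm was assigned. The Cycling arm was to receive "30 minutes/ day of in-bed cycling in addition to routine physiotherapy interventions, 5 days per week", and cycling ran to a maximum of 28 days or "stopped when the patient could march on the spot for 2 consecutive days", if that came first. For the comparator, "Patients received routine physiotherapy interventions per current institutional practice".

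Section 4.2.1 lists when the randomised intervention was not planned. One item, the marching milestone, applies to the Cycling arm only. The same section gives ergometer breakdown as a reason why a Cycling patient did not receive the randomised intervention on an eligible day.

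Section 6.1 reports adverse events "if they occurred during or immediately after in-bed cycling or routine physiotherapy interventions", provided that the clinical team attributed them to the randomised intervention and that the patient deteriorated clinically. The severe events include "fall to knees during routine PT/ rehabilitation activities".

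**The concern.** The label for the day set is the same in both arms, but its content is not. A Routine patient who has started to march and then has physiotherapy stays in the safety set. A Cycling patient in the same state, having the same physiotherapy after cycling has stopped, appears to leave it. The filter therefore depends on the arm. It also depends on recovery: if cycling speeds recovery, as the superiority hypothesis in section 3.4 expects, more Cycling-arm days are removed.

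Section 6.1 counts events during routine physiotherapy as well as during cycling, and section 6.5 then removes part of that experience in one arm. At stake is the between-group safety summary. Cycling could show fewer patients with events although the risk was the same. No other safety analysis in the SAP covers the omitted days.

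**Working it through.** **Step 1: does a Cycling-arm day need cycling to count?** The SAP does not say so outright, but two items in section 4.2.1 point that way.
- After the marching milestone the randomised intervention is not planned in the Cycling arm. Section 3.2 makes this milestone a stopping point for cycling and says nothing of routine physiotherapy stopping.
- Ergometer breakdown makes an eligible day a missed opportunity. If physiotherapy alone were enough, a broken ergometer would not by itself cause a miss.

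**Step 2: what happens to an event on each kind of day?** Take an event that meets all the conditions of section 6.1.

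| Day | Meets 6.1 | Counted under 6.5 |
|---|---|---|
| Routine arm, physiotherapy | yes | yes |
| Cycling arm, cycling given | yes | yes |
| Cycling arm, physiotherapy only | yes | no, on the reading in step 1 |

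**Step 3: direction and size.** The SAP gives no safety figure to reproduce. Let N be patients per arm, D rehabilitation days per patient, f the share of Cycling-arm rehabilitation days with physiotherapy only, rC the event risk on a cycling day and rP the risk on a physiotherapy-only day.
- Events, all rehabilitation days: N × D × [(1 − f) × rC + f × rP]
- Events, as counted: N × D × (1 − f) × rC
- Events lost: N × D × f × rP, which is never negative
- Share of patients with an event, all days: 1 − (1 − rC)^(D(1 − f)) × (1 − rP)^(Df)
- Share of patients, as counted: 1 − (1 − rC)^(D(1 − f))
- Share of days, as counted minus all days: rC − [(1 − f) × rC + f × rP] = f × (rC − rP)

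N = 180 follows from 360 patients randomised 1:1 (section 3.1). D = 10, the daily risks and f are assumptions.

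*No true difference, rC = rP = 0.5%.* The Routine arm has 180 × 10 × 0.005 = 9.0 events, and 1 − 0.995^10 = 4.9% of patients have one.

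| f | Cycling events counted | Cycling patients with an event | Share of days |
|---|---|---|---|
| 10% | 180 × 9 × 0.005 = 8.1 | 1 − 0.995^9 = 4.4% | 0.50% |
| 20% | 180 × 8 × 0.005 = 7.2 | 1 − 0.995^8 = 3.9% | 0.50% |
| 40% | 180 × 6 × 0.005 = 5.4 | 1 − 0.995^6 = 3.0% | 0.50% |

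Counting all rehabilitation days restores 9.0 events and 4.9%.

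*Unequal risks, f = 20%.*
- rC = 0.5%, rP = 1.0%: the share of days is 0.8 × 0.5% + 0.2 × 1.0% = 0.60% on all days against 0.50% counted. Events are 10.8 against 7.2.
- rC = 1.0%, rP = 0.5%: the share of days is 0.8 × 1.0% + 0.2 × 0.5% = 0.90% on all days against 1.00% counted. Events are 16.2 against 14.4.

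The event count falls in both cases. The per-day share moves in opposite directions.

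**The case against.** **The reading is inferred.** The SAP never classes a physiotherapy-only day in the Cycling arm. Section 6.5 describes its days as those at risk from rehabilitation, which such a day would fit, and Supplement Table 1 shows cycling plus routine physiotherapy as one entry up to ICU discharge. This stands as a caveat. Section 4.2.1 favours the stricter reading, and if the other was meant, section 6.5 still needs to say so.

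**Exposure-based safety sets are legitimate.** The restriction is stated openly with a reason, and the harms summary is descriptive with no test. That is fair, but the reason given is exposure to rehabilitation, and on the stricter reading the day set does not match that exposure in the Cycling arm.

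**Section 6.1 filters the events.** Each must be attributed to the randomised intervention and involve deterioration. This narrows the loss without removing it, because routine physiotherapy is part of the Cycling assignment.

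**Many missed days may be harmless here.** Patient or therapist factors can occur in either arm and may mean no physiotherapy at all. Of the examples listed, only equipment failure is specific to cycling. This limits f from missed days but does not touch days after the milestone.

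**Two stronger readings are tempting, and the SAP does not support them.**
- A reader might infer that the whole harms comparison favours cycling. For the per-day percentage this fails: numerator and denominator shrink together, and at equal daily risk the bias is zero.
- A reader might infer that nearly all falls in the Cycling arm are lost because patients are upright only once cycling has ended. Section 3.2 contradicts this. Cycling stops only after marching has been achieved on two days running, so standing and first marching happen while cycling is still planned. Falls in physiotherapy on days with cycling are counted.

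**Conclusion.** The concern holds for the number of events and of patients with events. On the reading that section 4.2.1 supports, these can only be unchanged or too low in the Cycling arm, while the Routine arm loses nothing in the same way. The same holds for the percentage of patients if its denominator is all randomised patients. Section 6.5 does not state that denominator, but section 4.3 points to it.

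The claim does not extend to the percentage of days with events, whose bias is f × (rC − rP) and can take either sign or be zero.

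The size is unknown, because the SAP gives neither the share of physiotherapy-only days nor the event risks. At equal daily risk the share of Cycling events lost equals f. The fall from 9.0 events to between 8.1 and 5.4 shows scale under assumed inputs and is not an estimate for this trial. The primary outcome is not affected. The point is worth correcting because the filter differs by arm and the remedy is cheap.

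**What to change.** In section 6.5:
1. Define days at risk identically in both arms, as any ICU study day with in-bed cycling or routine physiotherapy.
2. Report all events that meet the section 6.1 definition on those days by randomised group, and by activity (cycling or physiotherapy) where this was recorded. State that all randomised patients form the patient-level denominator.
3. Keep the present analysis of days with the randomised intervention as supplementary, and state whether a Cycling-arm day with physiotherapy alone counts in it.

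The cost is SAP wording and one more table. The Cycling per-day rate may change in either direction. The change also relies on the daily case report forms having captured events on physiotherapy-only days. Supplement Table 1 schedules "Study-related Serious Adverse and Adverse Events" for daily documentation, which suggests that the data exist but does not prove it. Completeness should be checked first, and any gap reported. No rule on delivering or stopping cycling needs to change.

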6.6 Statistical software

All analyses will be performed using the most current version of SAS 9.4 (Cary, NC).


Exclusion Criteria
 
 1. Acute condition impairing patients' ability to cycle (e.g., leg fracture) 2. Acute proven or suspected neuromuscular weakness affecting the legs (e.g., stroke or Guillain-Barré syndrome) 3. Traumatic brain injury 4. Inability to follow commands in local language pre-ICU 5. Severe cognitive impairment pre-ICU 6. Temporary pacemaker (internal or external) 7. Pregnant (or suspected pregnancy) 8. Expected hospital mortality $>90\%$ 9. Body habitus unable to fit the bike (e.g., leg amputation, morbid obesity) 10. Specific surgical exclusion as stipulated by surgical or ICU team 11. Palliative goals of care 12. Able to march on the spot at the time of screening 13. Persistent therapy exemptions in the first 4 days of mechanical ventilation: 
 i. Increase in vasopressor/ inotrope within the last 2 hours ii. Active myocardial ischemia, or unstable/ uncontrolled arrhythmia per ICU team iii. Mean arterial pressure <60 or >110 mmHg or per treating team within the last 2 hours iv. Heart Rate <40 or >140 bpm within the last 2 hours v. Persistent SpO₂ $<88\%$ or per treating team within the last 2 hours vi. Neuromuscular blocker within the last 4 hours vii. Severe agitation (Richmond Agitation and Sedation Scale >2 [or equivalent] [20]) within last 2 hours viii. Uncontrolled pain ix. Change in goals to palliative care x. Team perception that in-bed cycling or physiotherapy is not appropriate for other new reasons (e.g., acute peritonitis, new incision/wound, known/suspected muscle inflammation (e.g., rhabdomyolysis))

Eligible, non-randomized exclusion criteria
 
 1. Enrolled previously in CYCLE RCT or related study 2. Patient unable to give consent and no substitute decision maker (SDM) identified 3. Patient or SDM declines consent 4. ICU Physician declines patient or SDM to be approached 5. Other, specified by attending team

Table 2: Description of Primary outcome measure and analyses

Analysis of Primary Outcome	Description of Outcome	Measurement Timing	Analysis
Primary Outcome: Physical Function ICU Test-scored ^{1,2}	Based on 4 patient activities: arm strength, leg strength, ability to stand, and step cadences. Total scores range from 0 to 10 with higher scores meaning better function.	3 days after ICU discharge	Linear regression, adjusted for age and clinical site
Summary of subgroup and sensitivity analyses of the primary outcome			
Objective	Hypothesis	Analysis	
Subgroup Analyses			
i. To determine if age modifies the effect of cycling plus routine PT versus routine PT alone on the primary outcome.	Cycling will be more effective in older patients than in younger patients.	Linear regression adjusted for age and clinical site, which also includes a term for the interaction between age (≥ 65 versus < 65 years) and randomized allocation	
ii. To determine if baseline clinical frailty modifies the effect of cycling plus routine PT versus routine PT alone on the primary outcome.	Cycling will be more effective in patients with baseline frailty than in patients without baseline frailty.	Linear regression adjusted for age and clinical site, which also includes the main effect of frailty (≥ 5 versus < 5) and a term for the interaction between frailty and randomized allocation	
iii. To determine if sex modifies the effect of cycling plus routine PT versus routine PT alone on the primary outcome.	Cycling will be more effective in male than in female patients.	Linear regression adjusted for age and clinical site, which also includes the main effect of sex and a term for the interaction between sex and randomized allocation	
Sensitivity Analyses			
i. To account for ICU mortality on the primary outcome.	Accounting for mortality will not change the effect of cycling on the primary outcome.	Linear regression, adjusted for age and clinical site. All patients will be included. Those who died prior to 3 days post-ICU	

		discharge will be assigned a PFIT-s score of 0.
ii.	To determine the effect of cycling plus routine PT versus routine PT alone including only blinded assessment of primary outcome.	Including only patients with blinded assessment of the primary outcome will not change the effect of cycling on the primary outcome.
iii.	To determine the effect of cycling plus routine PT versus routine PT alone under maximal protocol conditions.	Cycling will more greatly be associated with increased function in patients with higher protocol adherence.
iv.	To determine the effect of cycling plus routine PT versus routine PT alone in those patients with completed assessment of the primary outcome.	Including only patients with complete assessment of the primary outcome will not change the effect of cycling on the primary outcome.
v.	To determine if the cycling effect is affected by centre, we will conduct analysis adjusting for age only.	Excluding adjustment for clinical site will not change the estimated effect of cycling on the primary outcome.
		Linear regression, adjusted for age and clinical site. Only patients with blinded PFIT-s assessments will be included.
		Linear regression, adjusted for age and clinical site. Only patients who received the randomized intervention or had a temporary exemption on $\geq 80\%$ of planned intervention days will be included.
		Linear regression adjusted for age and clinical site. Only patients with a total score for the PFIT-s at 3 days post-ICU discharge will be included.
		Repeat the primary linear regression adjusted for age only (i.e., exclude clinical site)

Table 3: Description of Secondary outcome measures and analyses

Outcome	Description of Outcome	Measurement Timing	Analysis
Physical Function ICU Test [14, 15]	Patients complete 4 activities: arm strength, leg strength, ability to stand, and step cadences. Total scores range from 0 to 10 with higher scores representing better function.	ICU awakening, ICU discharge, hospital discharge	Includes survivors at each time point. Separate linear regressions for each timepoint, adjusted for age
Medical Research Council Sum Score [19, 49]	Standardized physical exam of 6 muscle groups (3 upper, 3 lower), using a 6-point scale (0=no contraction; 5= contraction sustained against maximal resistance), summed to a total score. Total scores range from 0 to 60 with higher scores representing more strength.	ICU awakening, ICU discharge, 3 days after ICU discharge, hospital discharge	Includes survivors at each time point. Separate linear regressions for each timepoint, adjusted for age
Medical Research Council Sum Score, categorized as <48 versus ≥ 48 [19, 49]	Standardized physical exam of 6 muscle groups (3 upper, 3 lower), using a 6-point scale (0=no contraction; 5= contraction sustained against maximal resistance), summed to a total score. Total scores range from 0 to 60 with higher scores representing more strength	ICU awakening, ICU discharge, 3 days after ICU discharge, hospital discharge	Includes survivors at each time point. Separate logistic regressions for each timepoint, adjusted for age
30 second sit to stand test [26, 50]	Patient completes as many full sit to stand repetitions as possible within 30 seconds. Higher scores represent better strength.	ICU awakening, ICU discharge, 3 days after ICU discharge, hospital discharge	Includes survivors at each time point. Separate linear regressions for each timepoint, adjusted for age
2-minute walk test [28, 51]	Patient walks as far as possible over 2 minutes. Higher scores represent better endurance.	ICU discharge, 3 days after ICU discharge, hospital discharge	Includes survivors at each time point. Separate linear regressions for each timepoint, adjusted for age

Outcome	Description of Outcome	Measurement Timing	Analysis
Intensive Care Psychological Assessment [31]	Patients answer 10 questions related to psychological distress in the ICU using a 3-point scale (0=no; 1=yes, a bit; 2=yes, a lot), summed to a total score. Total scores range from 0 to 20, with higher scores representing more distress.	Following ICU awakening assessment	Includes survivors. Linear regression, adjusted for age
Patient-reported functional score for ICU [52]	Patients answer 6 questions about their current perception of function, using an 11-point scale (0=unable to perform activity; 10=able to perform activity at same level as before ICU admission), summed to a total score. Total scores range from 0 to 60, with higher scores representing better function.	ICU discharge, hospital discharge, 90-days post-randomization	Includes survivors at each time point. Separate linear regressions for each timepoint, adjusted for age
Euro-QOL 5D 5L Index [35]	Patients answer 5 questions about their current perception of mobility, self care, usual activities, pain/discomfort, and anxiety/depression, scored according to a prescribed algorithm. Higher scores represent better perceptions of health.	ICU discharge, hospital discharge, 90 days post-randomization	Includes survivors at each time point. Separate linear regressions for each timepoint, adjusted for age
Euro-QOL Visual Analogue Scale [35]	Patients rate their overall health on a 100-point visual analogue scale (0= worst health; 100= best health).	ICU discharge, hospital discharge, 90 days post-randomization	Includes survivors at each time point. Separate linear regressions for each timepoint, adjusted for age
Katz Activities of Daily Living scale [38]	The patient's ability to complete 6 tasks: bathing, dressing, toileting, feeding, continence, and bed mobility. A rater assesses whether the patient is dependent or independent according to pre-specified criteria. Total scores range from 0 to 6,	ICU discharge, hospital discharge	Includes survivors at each time point. Separate linear regressions for each timepoint, adjusted for age

Outcome	Description of Outcome	Measurement Timing	Analysis
	with higher scores representing better function.		
Clinical Frailty Scale [37]	Frailty includes a reduction in physical reserve and loss of function across multiple body systems. The clinical frailty scale is a 9-point scale, with higher scores representing more frailty.	Hospital discharge, 90 days post-randomization	Includes survivors at each time point. Separate linear regressions for each timepoint, adjusted for age
ICU Length of Stay	Days in ICU	ICU discharge	Linear regression, adjusted for age
Hospital Length of Stay	Days in hospital	Hospital discharge	Linear regression, adjusted for age
Mortality	Death	ICU discharge, hospital discharge, 90 days post-randomization	Separate Cox proportional hazards models for each timepoint, adjusted for age
Hospital Discharge Location	Same or better living location at hospital discharge from baseline	Hospital discharge	Includes survivors. Logistic regression, adjusted for age

Table 4: PFIT-s Scoring (adapted from Denehy et al.)[14]

	PFIT-s Component value score			
	0	1	2	3
Shoulder strength	MRC grade 0, 1, or 2	MRC grade 3	MRC grade 4	MRC grade 5
Knee Strength	MRC grade 0, 1, or 2	MRC grade 3	MRC grade 4	MRC grade 5
Sit-to-Stand assistance	Unable	Assist of 2 people	Assist of 1 person	No assistance
Step Cadence	Unable	>0 to 49	50 to <80	>80

MRC = Medical Research Council strength grade (0 to 5)

Supplement Table 1: Summary of Assessments

	Study Period							
	Enrolment	Allocation	Post-allocation					
Timepoint	ICU admission	0	In ICU	ICU awakening	ICU D/C	3 days post-ICU D/C	Hospital D/C	90 days post-randomization
Enrolment:								
Eligibility screening	X							
Informed consent	X							
Allocation		X						
Interventions:								
In-bed cycling + routine PT			X	X	X			
Routine PT			X	X	X			
Assessments:								
Severity of illness: APACHE II [53]	X							
Charlson Comorbidity Index[54]	X							
Functional Comorbidity Index[55]	X							
Clinical Frailty Scale [37]	X						X	X
Function: Katz Activities of Daily Living scale[38]	X				X		X	
Patient-reported functional scale for the ICU [56]					X		X	X
Physical Strength and Function:				X	X	X (blinded)	X (blinded)	
Physical Function ICU Test (scored)[14, 15]				X	X	X (blinded, Primary)	X (blinded)	
Medical Research Council Sum Score[49]				X	X	X (blinded)	X (blinded)	
30-second sit to stand[26]				X	X	X (blinded)	X (blinded)	

CYCLE Statistical Analysis Plan

	Study Period							
	Enrolment	Allocation	Post-allocation					
Timepoint	ICU admission	0	In ICU	ICU awakening	ICU D/C	3 days post-ICU D/C	Hospital D/C	90 days post-randomization
2-minute walk test[28]					X	X (blinded)	X (blinded)	
Psychological distress: Intensive Care Psychological Assessment Tool [31]				X				
Health-related Quality of Life: Euro-QOL 5D-5L[33, 34]					X		X	X
Hospital Anxiety and Depression Scale [36]								X
Data Collection:								
Baseline demographics	X							
Co-interventions			Document daily on CRFs					
Study-related Serious Adverse and Adverse Events			Document daily on CRFs					
Duration of mechanical ventilation								
ICU and Hospital Length of Stay							X	
Mortality					X		X	X

Supplement 2: Scoring algorithm for incomplete data in the PFIT-s

To account for incomplete component data in the PFIT-s, we will concurrently consider data from the PFIT-s, 30s sit-to-stand, and 2-minute walk tests at 3 days post-ICU or relevant time point (i.e., ICU awakening, ICU discharge, hospital discharge). For each patient with incomplete PFIT-s component data, we will evaluate the item within the context of the other scored PFIT-s items. For example, if a patient had a knee strength PFIT-s score of 1 or less (reflecting a Medical Research Council score of 3 or less and representing an inability to complete movement against gravity with any resistance), and had incomplete data for the sit-to-stand assistance component, then we would code sit to stand a score of 0, as this patient would likely not have the strength to stand. Likewise, if a patient completed the sit-to-stand component, needed assistance from 2 or more people, and data for step cadence were incomplete, we would assign step cadence a score of 0, as this patient would likely not have the strength to take any steps. In contrast, if a patient required 1 person to stand, and data for step cadence were incomplete, we would code this as missing data, as we do not have enough information to assess this patient's ability to perform the assessment.

To reduce bias, two research personnel will be blinded to the patient's randomized allocation and clinical site. The research personnel will only evaluate patients with incomplete data. We will document the rationale for all decisions in the study analytic data set. The two research personnel will aim for consensus, however if there is disagreement, we will invite a third clinical research coordinator to make a final judgement. We will use the following scoring algorithm based on a patient's observed function (Table S2):

Table S2: PFIT-s scoring algorithm

		PFIT-s Component value scored if incomplete			
	Observed	Shoulder strength	Knee strength	Sit-to-Stand Assistance	Step Cadence
PFIT-s Components:					
Shoulder strength	Any	N/A	Missing	Missing	Missing
Knee Strength	0 (MRC grade 0, 1, or 2)	Missing	N/A	0 (unable)	0 (unable)
	1 (MRC grade 3)	Missing	N/A	0 (unable)	0 (unable)
	2 (MRC grade 4)	Missing	N/A	Missing	Missing
	3 (MRC grade 5)	Missing	N/A	Missing	Missing
Sit-to-Stand assistance	0 (unable)	Missing	Missing	N/A	0 (unable)
	1 (assist of 2 people)	Missing	Missing	N/A	0 (unable)
	2 (assist of 1 person)	Missing	Missing	N/A	Missing
	3 (no assistance)	Missing	Missing	N/A	Missing
Step Cadence	Unable	Missing	Missing	Missing	N/A
	Able to clear their foot more than once	Missing	Missing	Missing	N/A

		PFIT-s Component value scored if incomplete			
	Observed	Shoulder strength	Knee strength	Sit-to-Stand Assistance	Step Cadence
Other Performance-based outcomes:					
30s Sit to Stand	1 or more repetitions; assistance of 2 or more people	Missing	Missing	1 (assist of 2 people)	0 (unable)
2-minute walk	Any score >0 m	Missing	Missing	Missing	Missing
	Any score >0 m and information re: assistance	Missing	Missing	Missing	Missing

N/A = not applicable; MRC = Medical Research Council strength grade (0 to 5)

Supplement 3: Scoring algorithm for incomplete data in the 30 Second Sit to Stand and 2-minute walk tests

30 Second Sit to Stand (30STS): We will review the 30STS within the context of the knee strength and sit-to-stand assistance components of the PFIT-s at each corresponding time point. If a patient had a knee strength PFIT-s score of 1 or less (reflecting a Medical Research Council score of 3 or less and representing an inability to complete movement against gravity with any resistance) and had missing data for 30STS, then we would code a score of 0 repetitions, as this patient would likely not have the strength the stand. If a patient received a sit-to-stand PFIT-s item score of 0 (representing inability to stand even with assistance), we will code the 30STS a score of 0, representing 0 repetitions since this patient cannot stand.

2-minute walk test (2MWT): We will review the 2MWT within the context of the knee strength, sit-to-stand assistance, and step cadence components of the PFIT-s at each corresponding time point. If a patient had a knee strength PFIT-s score of 1 or less, then we would code the 2MWT a score of 0 m, as they likely do not have the strength to stand or walk. If a patient completed sit-to-stand and required assistance from 2 or more people, and data for 2MWT was missing, we could code the 2MWT a score of 0, as this patient would likely not have the strength to walk. If a patient received a PFIT-s step cadence score of 1 or higher (representing ability to take at least 1 step) and data for the 2MWT was missing, then we would code this as missing data, as the patient may have been able to walk some distance.

We will use the same procedures to reduce bias, as described in Supplement 2 for the PFIT-s. We will use the following scoring algorithm based on a patient's observed function (Table S3):

Table S3: 30s Sit to Stand and 2-minute walk scoring algorithm

		Score if incomplete	
PFIT-s Component	Observed	30s Sit to Stand repetitions	2-minute walk distance
Shoulder strength	Any	Missing	Missing
Knee Strength	0 (MRC grade 0, 1, or 2)	0	0
	1 (MRC grade 3)	0	0
	2 (MRC grade 4)	Missing	Missing
	3 (MRC grade 5)	Missing	Missing
Sit-to-Stand assistance	0 (unable)	0	0
	1 (assist of 2 people)	Missing	0
	2 (assist of 1 person)	Missing	Missing
	3 (no assistance)	Missing	Missing
Step cadence	0 (unable)	Missing	0
	Able to clear their foot more than once	Missing	Missing

Legend: MRC = Medical Research Council Score
